### **11.2 PRODUCT COMPLAINT/DEVICE DEFICIENCY DEFINITION**

A product complaint/device deficiency is defined (21 CFR 820.3(b) and ISO 14155) as any alleged deficiency related to the identity, quality, durability, reliability, safety, effectiveness, or performance of a device. This may include malfunctions, use error, and inadequacies in labeling. Product complaints can pertain to any marketed JJSV device being used in the study. The investigator is to assess whether the deficiency could have led to a serious adverse event without suitable action or intervention or under less fortunate circumstances.

### **11.3 ADVERSE EVENT AND COMPLAINT REPORTING REQUIREMENTS**

All adverse events and any complaint encountered using any JJSV product, regardless of severity and whether attributed to the study device(s), are to be reported to JJSV and recorded on the case report form corresponding to the visit during which awareness of the event occurred. Adverse events are also to be reported to the reviewing IRB as per the IRB’s reporting requirements. If required, adverse events will be reported to the appropriate regulatory agencies (e.g., FDA) according to all applicable laws and regulations.

Reporting of adverse events shall follow the US Code of Federal Regulations (21CFR 812) for sites in the USA. Specific instructions on notification procedures to JJSV are included in **Appendix M**. General guidelines are provided below:

### **Adverse Event Reporting**

An adverse event that is not serious or device-related is to be reported to JJSV in a timely manner. Notification of non-serious and non-device related adverse events will occur by recording events on the CRF when noted. Such adverse events are also to be reported to the reviewing IRB per their reporting requirements.

### **Complaints/Device Deficiency Reporting**

A general product complaint or device deficiency is to be reported to JJSV in a timely manner. Notification of complaints/device deficiencies will occur by recording complaints on the CRF at the visit the complaint occurs (e.g., operative visit) and/or by a phone call/email to JJSV.

Any device deficiency that could have led to a serious adverse event without suitable action or intervention, or under less fortunate circumstances, must be reported to the sponsor immediately (no later than 24 hours after detection). Device deficiencies that could have led to a serious adverse event should also be reported to the investigator's IRB per their reporting requirements.

### **Serious and/or Device-Related Adverse Event Reporting**

SAEs and/or ADEs are to be documented using the Serious Adverse Event/Adverse Device Effect (SAE/ADE) CRF. In the event of an SAE, JJSV must be notified immediately (no later than 48 hours after detection). Any SAE/ADE is to be reported to JJSV by phone, email and/or by submitting the completed SAE/ADE CRF. Any SAE or device-related AE should also be reported to the investigator's IRB per their reporting requirements.

### **Unanticipated Adverse Device Effect (UADE)/Unanticipated Serious Adverse Device Effect (USADE) Reporting**

If during the study, a serious adverse event occurs that may reasonably be regarded as device-related and was not previously expected in nature, severity, or degree of incidence, the investigator is to report the UADE/USADE to JJSV within 48 hours, and to the investigator's IRB as soon as possible (and no later than 10 working days after learning of the event for sites in the USA as required by 21CFR812).

## **11.4 CAUSAL RELATIONSHIP**

The investigator should always be alert to adverse events that may be related to the study device or the use of the study device (i.e., the procedure specific to the initial application of the device). An attempt should be made in every case to determine the causality of the event. The following definitions are to be used as guidelines in determining the relationship between the event and the study device and/or use of the device.

- Definitely related: If the event is associated with the device and/or the use of the device beyond a reasonable doubt, a causal relationship exists between the adverse event and the device and/or the use of the study device.
- Probably related: There is a reasonable possibility of a causal relationship between the adverse event and the device and/or the use of the study device and/or the adverse event cannot be reasonably explained by another cause.
- Possibly related: The adverse event has not been determined to be related to the device or the use of the device, but no other cause has been identified and the device and/or the use of the study device cannot be ruled out as a possible cause.
- Unlikely to be related: The possibility of a potential causal relationship between adverse event and the device and/or the use of the device could exist, but the adverse event can be reasonably explained by another cause.
- Not related: There is no possibility of a causal relationship between the adverse event and the device and/or the use of the study device and/or the adverse event can be attributed to another cause.

If an adverse event is believed to be definitely, probably or possibly related to the study device and/or the use of the device, the event will be considered related to the study device and/or the use of the device.

### 11.5 ADVERSE EVENT FOLLOW-UP

For every adverse event, appropriate measures should be undertaken to treat and/or monitor the subject until resolution occurs. The subject's files are to include all pertinent medical data relating to the event including the subject's medical records, medical reports and/or judgments from colleagues or outside specialists who assisted in the treatment and follow-up of the subject. The investigator should keep JJSV closely informed as to the outcome of serious and/or device-related adverse events, thereby allowing JJSV to comply with the appropriate regulatory reporting requirements. An SAE/ADE CRF should be completed each time the subject returns to the investigator or other specialist(s) for follow-up of a serious and/or device-related adverse event until resolution of the event. Any subject who is to be exited from the study due to a serious and/or device-related adverse event should be followed until the outcome is determined prior to being exited from the study.

## 12. PROTOCOL CHANGES/AMENDMENTS

If the investigator wishes to modify any procedure and/or the design of the study, he or she must contact and obtain consent from JJSV regarding the proposed changes prior to implementation. Any modifications (including additional data collection) require approval by the governing IRBs prior to implementation.

## 13. ETHICS REVIEW AND PATIENT WELFARE

### 13.1 INSTITUTIONAL REVIEW BOARD (IRB)

It is the responsibility of the investigator to obtain prospective approval of the study protocol, protocol amendments or changes, ICF and other relevant documents (e.g., advertisements) from the IRB. All correspondence with the IRB should be retained in the Investigator Study Files/Notebook. Copies of IRB submissions and approvals should be forwarded to JJSV.

The investigator is responsible for notifying the IRB of reportable adverse events as well as any other circumstance in which additional procedures outside the protocol were conducted to eliminate apparent hazards to subjects.

### 13.2 INFORMED CONSENT

The current version of the IRB-approved study ICF must be signed by each study subject prior to any study-specific examinations being performed. The IRB-approved ICF is to be signed and dated by the subject as well as by the person who conducted the informed consent discussion. The signed ICF will be maintained by the investigator as a permanent part of the subject's medical records. A copy of the signed and dated form is to be provided to the subject. The investigator will provide JJSV written acknowledgement on the preoperative case report form that a signed agreement of informed consent has been obtained and is in the investigator's possession for each subject. As required by 21CFR 812 Part G, the site shall document in the source documents that informed consent was obtained prior to participation in the study for each subject enrolled.

**NOTE:** *The informed consent process also includes obtaining the subject's signature on an Authorization for Use/Disclosure of Health Information for Research Form or equivalent documentation necessary to comply with applicable privacy laws pertaining to medical treatment in the governing countries.*

**NOTE:** *The sponsor will secure appropriate insurance for study subjects prior to study start.*

## 14. DOCUMENTATION

### 14.1 SOURCE DOCUMENTS

Source documents must be kept for all study subjects. Source documents may include a subject's medical records, hospital charts, clinic charts, the investigator's subject study files, as well as results of any diagnostic tests or procedures such as topographies or laboratory tests with photographs or instrument printouts.

Each site is expected to adhere to the clinic's own standard documentation requirements for medical charts/clinic notes. For the purposes of this clinical study, the medical charts/clinic notes must also include, at a minimum, the following data that will be considered source data and will be reviewed by the Sponsor:

- Subject's name and study identification number
- Subject's contact information
- Study protocol number and the Sponsor name (JJSV)
- A statement that informed consent was obtained prior to participation in the study (including the date)
- Evidence of subject eligibility
- Dates of all subject visits and surgeries throughout the duration of the study
- Implant serial number identification
- Concurrent medications
- Corrected and uncorrected distance visual acuity
- Manifest refraction
- Occurrence and status of any operative complications, postoperative medical or lens findings and adverse events
- Occurrence and status of any subject complaints, e.g., ocular/visual symptoms
- The date the subject exited the study, and a notation as to whether the subject completed the study or reason for early exit.

#### **14.2 SUBJECT CONFIDENTIALITY**

Subjects will be assigned a site/subject number to maintain subject confidentiality. Subject names may possibly be disclosed to JJSV or regulatory agencies during inspection of medical records related to the study, but reasonable precautions will be taken to maintain confidentiality of personal information to the extent permitted by applicable laws and regulations.

#### **14.3 CASE REPORT FORM COMPLETION**

This study will use an electronic data capture system. All study staff responsible for entering data into the system must complete certification prior to using the system. The investigator is responsible for ensuring that data are properly recorded on each subject's case report forms and related documents. Prior to database lock, the investigator will verify completeness and accuracy of data submitted to the Sponsor.

#### **14.4 STUDY SUMMARY**

A final investigator's summary (study close-out) will be provided to the reviewing IRB after termination or the completion of the study or the investigator's part of the study, as directed by the Sponsor.

## **15. MONITORING**

The Sponsor will perform three types of monitoring to ensure compliance with regulations: data monitoring, administrative monitoring, and safety monitoring.

### **15.1 DATA MONITORING**

In order to ensure a well-controlled clinical trial, the Sponsor will follow specific data monitoring procedures, routinely generate reports and periodically review safety and effectiveness data. To avoid bias, any analyses generated prior to site closures will not be disseminated to any of the investigative sites.

An electronic data capture system (EDC) will be used to transmit case report forms from the investigative site to the Sponsor. Requests for data clarification will be handled through this same system.

To minimize data omissions and inconsistencies on clinical reports and to ensure that data are accurately transcribed to computer data files, the Sponsor will follow internal data processing procedures that include automated and manual quality control checks to identify any data discrepancies. Any such items will be resolved and documented as needed in EDC.

#### **Prevention of Missing Data**

Methods used to safeguard against missing data that can have deleterious effects on the study integrity and reliability of its outcomes will include training study staff with WebEx/Skype, centralized and/or on-site programs. In addition, subjects will be encouraged at the time of informed consent to avoid missing study visits, as missing data may affect the study reliability and diminish the scientific value of their contribution to the study.

### **15.2 ADMINISTRATIVE MONITORING**

Administrative monitoring procedures will ensure that study devices, subjects, and forms can be traced and will allow monitoring of investigator progress and compliance. Accountability and traceability of study devices will be monitored by trained Sponsor personnel.

#### **Site Monitoring Plan**

Prior to performing any study implants, the requirements of the study and reporting mechanisms will be explained to each investigator either personally at the investigative site or at a formal study investigator meeting. When necessary, a pre-study site qualification visit may be performed to assess the adequacy of the site to perform the study for sites that have not previously worked with the Sponsor or have undergone significant changes or have not been visited in the past year. An initial site visit will be conducted prior to the first implant for all sites.

Throughout the duration of the study, site visits to monitor compliance to this protocol will be made at each investigative site. During interim site monitoring visits, the Sponsor will review informed consent documents and subject eligibility, and the data on study case report forms will be verified against subject charts and other source documents to ensure complete and accurate reporting.

The subject files will also be reviewed to assure that all adverse events and any issues encountered with JJSV products have been reported in a timely fashion.

The Sponsor will also review source documents to verify that all required items have been documented in the subject medical charts. Refer to **Section 14.1**, Source Documents, for a list of items that are required for source documentation. In addition to subject files, study logs will be checked to ensure compliance with study procedures.

Additional training on study-specific procedures may also be conducted during monitoring visits.

Upon study completion, a final close-out site visit will be made to each site to monitor the last of the subject data records and finalize any outstanding study issues.

A separate Study Monitoring Plan will be established prior to study start that will define the type and frequency of monitoring visits and frequency of record monitoring.

## **16. MEDICAL MONITORING**

The medical monitor will review results throughout the clinical trial as necessary to ensure the continued safety of the device and to ensure that no subjects are exposed to unreasonable risk. The medical monitor will be available to answer all questions from investigators. The medical monitor will review and assess any reports of serious and/or device-related adverse events as well as device deficiencies that could have led to a serious adverse event and discuss these with the reporting investigator(s) as necessary. The medical monitor, as well as any other qualified personnel designated by the Sponsor, shall also review study reports.

## **17. PUBLICATIONS**

Refer to the Clinical Trial Agreement for information regarding JJSV publication policies.

## **18. RISK ANALYSIS**

### POTENTIAL RISKS AND RISK MANAGEMENT

#### RISKS OF THE TECNIS® TORIC II INTRAOCULAR LENS

The acrylic 1-piece IOL TECNIS Toric II (ZCU Series) is designed to have improved rotational stability relative to the currently marketed TECNIS Toric 1-piece IOL (ZCT Series). The lenses are made from the same SENSAR soft acrylic material that is used in marketed TECNIS 1-piece lenses. Its aspheric anterior surface is intended to compensate for corneal spherical aberration.

The risk documentation for the currently marketed TECNIS 1-piece lenses, ZCB00 and ZCT Series, is applicable. For ZCB00 and ZCT lenses, current risk documentation concludes that all risks are identified as low or medium and deemed acceptable.

An additional risk assessment for the TECNIS Toric II was conducted to analyze potential hazardous situations resulting from the design differences compared to the ZCB00 and ZCT designs. With the implementation of a Risk Control Plan under this risk assessment, no additional

safety issues have been identified for the study products for their intended use in the proposed clinical investigation.

### GENERAL RISKS OF CATARACT SURGERY AND IOL IMPLANTATION

There are risks and complications associated with cataract surgery and IOL implantation in general. These can include worsening of vision, hemorrhage, loss of corneal clarity, inflammation, infections, retinal detachment, pupil changes, glaucoma, etc. Complications can result in poor vision, loss of vision or loss of the eye.

### RISK MANAGEMENT

Subjects will be closely monitored throughout the trial duration. The occurrence of adverse events and complaints will be assessed at each study visit and reported to JJSV according to **Section 11.0**, Adverse Events and Product Complaints. Additionally, JJSV will monitor incoming data following the procedures outlined in **Section 15.0**, Monitoring. The Medical Monitor will ensure subjects are not exposed to additional risks by monitoring serious adverse events, device-related adverse events, and device-deficiencies that could have led to serious adverse events (**Section 15.3**, Safety Monitoring).

### POTENTIAL BENEFITS

The general clinical performance of the TECNIS Toric II is expected to be similar to the TECNIS Toric ZCT lens series. The primary benefit from implantation of the TECNIS Toric II is the correction of astigmatism following removal of the natural crystalline lens due to cataract.

### CONCLUSION

The hazards/risks associated with the TECNIS Toric II are acceptable and within those of JJSV's currently marketed IOLs. The potential clinical benefits of the TECNIS Toric II IOL outweigh the residual risks when the devices are used as intended.

## **19. RECORDS RETENTION**

All study-related correspondence, subject records, consent forms, Authorization for Use/Disclosure of Health Information Forms or similar medical treatment privacy law documentation, records of the distribution and use of all study products, and original case report forms should be maintained by the investigator.

The investigator must maintain and have access to the following essential documents until notified by the Sponsor.

**NOTE:** *This may be for a minimum of 15 years after completion of the study. The Sponsor requires notification if the investigator wishes to relinquish ownership of the data so that mutually agreed-upon arrangements can be made for transfer of ownership to a suitably-qualified, responsible person.*

- All case report forms within the EDC system
- All adverse event information (i.e., medical records, medical reports and/or judgments from colleagues or outside specialists who assisted in the treatment and follow-up of the subject)
- Study lens supply records/inventory
- IRB approval documentation
- Study correspondence
- Study agreements
- Site visit documentation
- Protocol(s) and the reason for any deviations from the protocol
- Subject log(s)
- Completed subject ICFs and HIPAA authorizations
- Subject medical chart/clinic notes

## **20. TERMINATION OF THE INVESTIGATION**

JJSV can suspend or terminate the clinical investigation at any time for reasons it determines appropriate. Additionally, the investigator, or JJSV, may stop a subject's participation at any time. However, no suspension of the study would be made to disadvantage the study subjects. Following suspension of the study for any reason, all study subjects who have already received treatment would continue to be followed through completion of the study visit schedule.

## **21. STATISTICAL METHODS**

This section highlights the analyses to be performed for key study endpoints. 1-Week postoperative visit will be the key timeframe for rotational stability. The final 3-month postoperative visit will be the key timeframe for visual acuity, refraction and questionnaire. Data from other study visits (other than key timeframe) may be reported for supportive analysis. All complications and adverse events will be evaluated at all visits.

Descriptive statistics will typically include mean, standard deviation, median, minimum, maximum for continuous data with frequency and proportion reported for categorical data.

### **21.1 ANALYSIS POPULATION**

For monocular endpoints, all eyes implanted with a study toric IOL (model ZCU150 through ZCU600) will be pooled together for analysis; which include both study eyes from bilaterally implanted subjects and one study eye from unilaterally implanted subjects. For binocular endpoints (i.e., binocular visual acuity and patient satisfaction questionnaire), only bilaterally

implanted subjects will be included for analysis. Available data will be used for analysis (i.e., no data imputation for missing data).

For the rotational stability endpoint, the primary analysis population will be all eyes implanted with a study toric IOL (model ZCU150 through ZCU600) and with available valid axis data at the 1-week visit.

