## 10.2 VISIT SCHEDULE

The study visit schedule for all study subjects is outlined in **Table 2**.

All subjects are intended to have unilateral or bilateral cataract surgery with the study lens. In bilateral subjects the second eye surgery should occur no more than 30 days after the first eye surgery. For both unilateral and bilateral subjects, after each surgery, the operative eye should be examined at 1 day (1-2 days), 1 week (5-14 days) and 3-months (60-120 days) postoperative. For bilateral subjects, based on the date of the second-eye surgery, both eyes should be evaluated at the same 3-month postoperative visit. Unscheduled visits may be conducted as necessary at the discretion of the investigator for medically-indicated follow-up.

TABLE 2: Visit Schedule

Visit	Eyes Evaluated	Exam	Visit Window
1	Both Eyes	Preoperative Exam	Within 60 days prior to 1 st surgery
2	First Eye	Operative	0-60 days after preoperative exam
3	First Eye	1 day	1-2 days postoperative
4	First Eye	1 week	5-14 days postoperative
5	Second Eye	Operative	No more than 30 days after 1 st eye surgery
6	Second Eye	1 day	1-2 days postoperative
7	Second Eye	1 week	5-14 days postoperative a
8	Both Eyes	3 months	60 - 120 days postoperative from 2 nd eye surgery a,b

a Subjects with a bilateral treatment, if both the 1st and 2nd eyes are within visit window, this visit may be done on the same day.

b If for any reason the second eye is not implanted, the first eye should be examined for the 3-month study visit 60 to 120 days following the first eye surgery.

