### BASELINE PHOTOGRAPH OF THE IOL POSITION

At the end of each case (regardless of whether repositioning was required), a minimum of 3 high-quality photographs should be taken through the surgical microscope showing the lens in its final position. Care should be taken to ensure clear visibility in the photo of both the scleral vessels and the lens axis marks as this will be the baseline image for all future rotation measurements. **Appendix C** provides detailed instructions for capturing photographs through the surgical microscope. If video capabilities are available, the surgeon should capture the entire surgery through the surgical microscope on video. If at the end of surgery, a high-quality image of the eye cannot be obtained for any reason, then a slit lamp photograph should be taken following surgery as a back-up.

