#### Secondary Surgical Interventions

Secondary surgical interventions due to refractive error and/or medical complications are serious adverse events. Secondary surgical interventions have become the standard of care in some cases and are considered to be in the subject's best interest. The clinical protocol will allow for secondary surgical interventions in the following categories:

- IOL repositioning due to a significant axis misalignment resulting in a visual outcome that is unsatisfactory, providing the axis misalignment is rotationally correctable.
- IOL exchange due to incorrect spherical power resulting in a significant decrease in uncorrected visual acuity.
- IOL exchange due to surgical or postoperative medical complications or adverse events.

If IOL repositioning procedure is required, the investigator should collect dilated slit lamp photograph showing IOL position prior to reposition.

**NOTE:** *If a toric IOL is repositioned, the subject will continue to be followed through study completion for safety. If a toric IOL is exchanged for a non-toric IOL, the subject should be followed until resolution of the serious adverse event/adverse device effect.*

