### **10.9 UNSCHEDULED VISITS**

During the study period, if a non-protocol-required visit is done for the purpose of medically-indicated follow-up for a study eye, data from this visit should be reported using the Unscheduled Visit CRF. The need for unscheduled visits is at the investigator's discretion. Specific examinations to be performed at unscheduled visits are also at the discretion of the investigator (based on the reason for the unscheduled visit) and data are to be recorded in the appropriate section of the CRF.

Data to be collected may include:

- Manifest refraction (using standard Snellen Chart)
- Uncorrected and best-corrected Snellen distance visual acuity
- Intraocular pressure
- Slit lamp examination for medical and/or lens findings

- Slit lamp photographs of IOL position
- Dilated or undilated fundus exam
- Ocular symptoms
- Adverse events
- Medications

If in the opinion of the investigator, IOL misalignment is suspected to be the cause of subjects' visual complaint at an unscheduled visit, the investigator should collect UCDVA, manifest refraction, BCDVA, Keratometry, non-directed visual symptoms, dilated slit lamp photographs (**Appendix I**) and lens axis orientation measurement (**Appendix J**).

***NOTE:** In the opinion of the investigator, if the estimated lens axis orientation remains unchanged since the last study visit, slit lamp photographs need not be repeated.*

Conditions found postoperatively, but previously documented at the preoperative visit, do not trigger an unscheduled visit report. However, if the severity of the condition increases from the preoperative visit, an Unscheduled Visit CRF is needed.

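### Sections 21.1 and 21.2 have no rule for an eye repositioned for misalignment before its 1-week photograph, so a lens that truly rotated can leave the primary failure count

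*Combined protocol and SAP*

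**What the plan says.** Section 21.1 defines the primary rotation population as "all eyes implanted with a study toric IOL (model ZCU150 through ZCU600) and with available valid axis data at the 1-week visit". It uses available data only and bars imputation. It does not define what makes axis data valid. Section 21.2 measures absolute rotation from the operative axis to 1 week on photographs and sets the success criterion at 90% of eyes within 5 degrees. Neither section mentions repositioning, exchange or removal.

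Section 10.7 (Secondary Surgical Interventions) permits "IOL repositioning due to a significant axis misalignment resulting in a visual outcome that is unsatisfactory", provided that rotation can correct it, and names no earliest day. It adds that "the investigator should collect dilated slit lamp photograph showing IOL position prior to reposition", and then: "If a toric IOL is repositioned, the subject will continue to be followed through study completion for safety". It does not say whether that photograph supplies the endpoint.

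Three other places bear on the point:
- Section 10.2 sets the windows: "the operative eye should be examined at 1 day (1-2 days), 1 week (5-14 days) and 3-months (60-120 days) postoperative".
- Section 10.6 says of the end-of-surgery photograph that "this will be the baseline image for all future rotation measurements".
- Section 10.9 says that when misalignment is suspected at an unscheduled visit, "the investigator should collect UCDVA, manifest refraction, BCDVA, Keratometry, non-directed visual symptoms, dilated slit lamp photographs", together with a slit-lamp axis reading. A note relaxes this: "if the estimated lens axis orientation remains unchanged since the last study visit, slit lamp photographs need not be repeated".

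**The concern.** Rotation beyond 5 degrees is the event the study is meant to count, and early repositioning is a consequence of that event. If repositioning decides whether an eye has a usable 1-week value, missingness depends on the outcome. Leaving out the missing eyes then favors the lens.

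The text leaves two readings for an eye repositioned before its 1-week photograph. It may lack valid 1-week axis data and be dropped, which is the likelier reading because its further follow-up is described as being for safety. Or its 1-week photograph, which shows the corrected position, may be accepted. Both remove a true failure.

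At stake are the reported proportion and its interval and, if the true rate is close to the criterion, the success statement.

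**Working it through.** **Inputs.** 200 evaluable eyes (Sections 8 and 21.5); expected proportion 95% (21.5); criterion 90% (21.2); 1-week window days 5-14 (10.2). Three assumptions are not in the documents: the number k of truly rotated eyes repositioned before their 1-week photograph (0 to 2 of 200), exact (Clopper-Pearson) intervals, and independent eyes.

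**Step 1: the plan's own figure.** Half-width = 1.96 × √(0.95 × 0.05 / 200) = 0.0302, or 3.0 points. Section 21.5 is reproduced with the normal approximation.

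**Step 2: timing.** A pre-reposition photograph taken on days 5-14 lies inside the 1-week window and can reasonably be read as the 1-week value, although no sentence says so. One taken before day 5 lies outside the window. No text lets it stand as the 1-week value, and the no-imputation rule points against it. The gap is therefore clear before day 5 and only a matter of wording after that.

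**Step 3: effect on the estimate.** With s true successes in 200, the correct proportion is s/200. Dropping k failures gives s/(200 − k). Scoring them after correction gives (s + k)/200. At s = 190:

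| k | Counted as failures | Dropped | Scored after correction |
|---|---|---|---|
| 0 | 190/200 = 95.0% (91.0-97.6) | same | same |
| 1 | 190/200 = 95.0% (91.0-97.6) | 190/199 = 95.5% (91.6-97.9) | 191/200 = 95.5% (91.6-97.9) |
| 2 | 190/200 = 95.0% (91.0-97.6) | 190/198 = 96.0% (92.2-98.2) | 192/200 = 96.0% (92.3-98.3) |

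Per eye, the shift is 190/199 − 190/200 = 0.48 point if dropped and 1/200 = 0.50 point if scored as a success. With two eyes dropped, the lower limit rises by 92.2 − 91.0 = 1.2 points, against a planned half-width of 3.0.

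**Step 4: effect on the 90% criterion.** Let X ~ Binomial(200, p) be the true successes. The criterion is met if X ≥ 180 when the eyes count as failures, X ≥ 0.9 × (200 − k) rounded up when they are dropped, and X ≥ 180 − k when they are scored as successes.

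| True p | Counted as failures | k = 1: dropped / scored | k = 2: dropped / scored |
|---|---|---|---|
| 0.89 | 38% | 38% / 47% | 47% / 56% |
| 0.90 | 56% | 56% / 65% | 65% / 73% |
| 0.95 | 99.9% | 99.9% / >99.9% | >99.9% / >99.9% |

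One dropped eye changes nothing, because 0.9 × 199 = 179.1 still requires 180 successes.

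**Step 5: the opposite direction.** The end-of-surgery image is the fixed baseline. A lens that never rotated but was surgically moved more than 5 degrees, and then photographed at 1 week, would be scored as rotated. Two such eyes would turn 190/200 into 188/200 = 94.0% (89.8-96.9).

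**The case against.** The best case against the point is that very few eyes can be affected. Section 10.7 reserves repositioning for a significant misalignment with an unsatisfactory visual result. Appendix A schedules no postoperative refraction or keratometry before 1 week, so a case before day 5 would usually come from an unscheduled visit. At the planned 95% there are about 10 failures in 200 eyes, and two early repositionings would be 2/10 = 20% of them. The study specifies no hypothesis test. Section 6.2 reports the repositioning and exchange rate, and Section 21.3 reports 1-day rotation, so these eyes are not hidden.

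All of that stands and limits the size. It does not supply the missing rule: separate reporting leaves the primary proportion uncorrected.

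A reader might infer more than the documents support:
- *The success conclusion is in doubt.* At the planned 95% it is not (Step 4).
- *Every repositioned eye is lost.* A photograph from days 5-14 can be read as 1-week data.
- *The bias only runs upward.* Step 5 shows a case that runs downward.
- *Exchange for misalignment is an equal route.* The exchange categories in Section 10.7 are incorrect spherical power and complications or adverse events. Only the reporting line in Section 6.2 contemplates exchange for misalignment.
- *A rule was lost.* The change history mentions a clarification on repositioned lenses at version 2.0. That log describes superseded text, and the point rests on the current sections alone.

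**Conclusion.** The gap is real and narrow. Following Sections 21.1 and 21.2 as written takes a lens that rotated more than 5 degrees, and was repositioned before day 5, out of the primary failures by one route or the other. Each such eye adds about 0.5 point. With an assumed 0 to 2 eyes in 200, the estimate at 95% moves by 0 to 1 point and the lower confidence limit by up to about 1.2 to 1.3 points. The 90% criterion is affected only if the true rate is near 90%: at a true 89% and two eyes, the chance of meeting it rises from 38% to 47% or 56%.

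The count is an assumption, since the documents give no repositioning rate. Independence of eyes and the exact interval are also assumptions. The direction for a truly rotated lens follows from the text and needs none of them. The rule should be fixed before the 1-week data are analyzed.

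**What to change.** State in Sections 21.1 and 21.2:

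1. An eye repositioned, exchanged or removed because of misalignment before its 1-week photograph stays in the primary denominator.
2. It is scored from its last analyzable photograph before the re-intervention, against the end-of-surgery baseline. If there are several, including two within days 5-14, the latest governs.
3. Axis data taken after a re-intervention are not used for rotation at any visit, including 3 months.
4. If the photograph taken for the re-intervention is missing or not analyzable, the slit-lamp axis reading made before it, or the 1-day photograph, is used if one exists. Otherwise the eye counts as more than 5 degrees, and the result without it is shown as a sensitivity analysis.
5. The number of eyes handled this way is reported, by the source of the value used.

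This concerns scoring only. Who is repositioned, and when, is unchanged.

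The cost is a short amendment with IRB approval (Section 12), a slightly lower reported proportion if such eyes occur, and two narrow, stated departures from the available-data rule: an earlier photograph used as the 1-week value, and the failure default. The fallbacks are imperfect. A slit-lamp reading is not the photographic method, a 1-day photograph may predate the rotation, and the failure default could misclassify an unrotated lens, hence items 4 and 5. Section 10.7 already asks for the photograph before repositioning, but not expressly before exchange or removal, so that request would need a few added words.
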